### 8.2.1 Disposition

Disposition status, along with reasons for discontinuation (from treatment as well as study) will be summarized by number and percentage of patients for the all enrolled patients.

### 8.2.2 Baseline demographics

Summaries of baseline demographic will include the following:

Gender, age at enrollment, race/ethnicity, country of birth, country of residence, country of origin, duration of ATTR amyloidosis symptoms at enrollment, time from symptom onset to diagnosis, age at onset of symptoms, follow-up time.

Summaries will be provided for the following sets: all enrolled patients, tafamidis treated set by phenotype at enrollment and overall, tafamidis untreated set by phenotype at enrollment and overall.

### 8.2.3 Disease characteristics

Summaries of disease characteristics will be provided for the following sets: all enrolled patients, tafamidis treated set by phenotype at enrollment and overall, tafamidis untreated set by phenotype at enrollment and overall.

Summaries will include CCI score at baseline, CCI whether or not the patient was diagnosed with ATTR amyloidosis, time since symptom onset, time since diagnosis, age at onset of symptoms, how diagnosis was made (symptoms, amyloid confirmed on biopsy, TTR confirmed as precursor protein, scintigraphy, other), prior misdiagnosis (Y/N), genotype (TTR mutation vs wild type), diagnosis type for the wild type subset, past or current clinical trial participation (Y/N), past or current Tafamidis Compassionate Use/Early Access or other non-commercial program (Y/N), family history (Y/N; as well as details – inherited from, method of diagnosis in affected family member, number of affected generations), number and percentage of patients with pacemakers at baseline, with the indication and type, number and percentage of patients with implantable cardiac defibrillator at baseline with indication (primary prevention of sudden death (Y/N), secondary prevention of sudden CCI CCI Heart failure, abnormal ECG, Atrial fibrillation/flutter, participation frequency (%) in tafamidis trial and non-tafamidis trial. A summary of misdiagnoses will also be provided for the following sets: all enrolled patients, tafamidis treated set by phenotype at enrollment and overall, tafamidis untreated set by phenotype at enrollment and overall.

### 8.2.4 Symptoms

The ongoing definitely related symptoms at enrollment/baseline, ongoing possibly related symptoms at enrollment/baseline, and ongoing symptoms at enrollment/baseline unrelated to TTR will be summarized by severity for the following sets: tafamidis treated set by phenotype at enrollment and overall, tafamidis untreated set by phenotype at enrollment and overall, and tafamidis treated set who are either predominantly cardiac or mixed phenotype at enrollment by CCI class at enrollment.

The past definitely related symptoms at enrollment/baseline, past possibly related symptoms at enrollment/baseline, and past symptoms at enrollment/baseline unrelated to TTR will be summarized by severity for the following sets: tafamidis treated set by phenotype at enrollment and overall, tafamidis untreated set by phenotype at enrollment and overall.

Symptoms developed post enrollment/baseline (defined as a symptom with an onset date after the date of enrollment for the untreated set and as a symptom with an onset date after the first dose of tafamidis for the treated subset) will be summarized by severity separately based on whether or not symptoms were definitely related, possibly related, or unrelated to TTR for the following sets: tafamidis treated set by phenotype at enrollment and overall, tafamidis untreated set by phenotype at enrollment and overall, tafamidis treated set who are either predominantly cardiac or mixed phenotype at enrollment by CCI class at enrollment, tafamidis treated set for patients who switched from predominantly cardiac to mixed phenotype, tafamidis treated set for patients who switched from predominantly neurologic to mixed phenotype, tafamidis untreated set for patients who switched from predominantly cardiac to mixed phenotype, tafamidis untreated set for patients who switched from predominantly neurologic to mixed phenotype.

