### **11.4. Definitions of Safety Events**

#### **11.4.1. Adverse Events**

An AE is any untoward medical occurrence in a patient administered a medicinal product. The event need not necessarily have a causal relationship with the product treatment or usage. Examples of AEs include but are not limited to:

- Abnormal test findings (see below for circumstances in which an abnormal test finding constitutes an AE);
- Clinically significant symptoms and signs;
- Changes in physical examination findings;
- Hypersensitivity;
- Progression/worsening of underlying disease;
- Lack of efficacy;
- Drug abuse;
- Drug dependency.

Additionally, for medicinal products, they may include the signs or symptoms resulting from:

- Drug overdose;
- Drug withdrawal;

- Drug misuse;
- Off-label use;
- Drug interactions;
- Extravasation;
- EDP;
- Exposure during breast feeding;
- Medication error;
- Occupational exposure.

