## 2.2 STUDY OBJECTIVES

The objectives of THAOS are to:

- Describe the population of patients affected with ATTR amyloidoses;
- Enhance the understanding of disease natural history, including the variability and progression of the hereditary and acquired forms of the disease;
- Better understand the genotype – phenotype relationship in ATTRv;
- Compare the progression of disease and overall survival in patients with ATTR amyloidosis with and without liver transplant;
- Foster an international community of medical experts who will develop recommendations on the clinical management of ATTR amyloidoses;
- Provide information to better understand the management and treatment of patients with ATTR amyloidoses through publication of the survey data;
- Provide information on off-label use of tafamidis by identifying patients who do not meet the inclusion criteria for transthyretin amyloid cardiomyopathy (ATTR-CM)
- For tafamidis-treated patients, collect and summarize all AE/SAE data, including for the specific safety concerns outlined in Table 1 Summary of Safety Concerns to be Assessed in THAOS comprising important identified risks, important potential risks, and missing information that includes long-term safety in ATTR-CM patients with **CCI** [REDACTED] Class IV.
- For patients not treated with tafamidis, collect and summarize additional data on the events of interest listed in Table 1.

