## 7 HANDLING OF MISSING VALUES

Missing observations will be treated as missing except for dates. For dates with missing days but not missing months, the 1st of the month will be imputed, and for dates with missing months and days, July will be imputed for months and the 15th will be imputed for days.

For any missing data (CCI [REDACTED]) corresponding to PRO, the PRO specific scoring manual will be utilized for imputation.

Patients with missing data for a variable will be excluded from the denominator when calculating proportions involving observed data for that variable.

If the tafamidis start day is missing, it will be imputed as the 15th of the corresponding month as per the eCRF guidelines. For date of birth, if only year is collected, then the day and month will be considered as 1st of January.

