## **8 STATISTICAL METHODOLOGY AND STATISTICAL ANALYSES**

### **8.1 STATISTICAL METHODS**

The key objectives of the survey are to better understand the natural history of ATTR (hereditary and wild-type forms) and the progression of disease in this patient population. Analysis of clinical outcomes will be conducted on all enrolled patients with available data. Outcomes will be examined separately for the untreated and tafamidis treated sets, as well as for appropriate subgroups within these set. Outcomes will include results of the key clinical, functional and QoL assessments used to define progression of disease.

Data will be summarized descriptively.

Continuous variables will be summarized using descriptive statistics ie, number of non-missing values and number of missing values [ie, n (missing)], mean, median, standard deviation (SD), minimum, maximum and 10th and 90th percentile.

Qualitative variables will be summarized by frequency counts and percentages. Unless otherwise specified, the calculation of proportions will be based on non-missing values.

In case the analysis refers only to certain visits, percentages will be based on the number of patients still present in the study at that visit, unless otherwise specified. Sample size in a subgroup needs to be at least 10 in order to have sufficient data to provide descriptive statistics, listings will be provided for smaller subgroups.

Kaplan-Meier estimates (product-limit estimates) will be presented including the median time with two-sided 95% confidence intervals (CIs), if the number of events are at least 5.

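### Post-baseline symptom percentages in SAP 8.2.4 have no at-risk denominator, so patients who already have a symptom lower its percentage, and columns with different baseline prevalence are not comparable

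*SAP*

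**What the plan says.** SAP 8.2.4 defines the untreated count as follows: "Symptoms developed post enrollment/baseline (defined as a symptom with an onset date after the date of enrollment for the untreated set". For treated patients the symptom is defined "as a symptom with an onset date after the first dose of tafamidis for the treated subset". The counted symptoms "will be summarized by severity separately based on whether or not symptoms were definitely related, possibly related, or unrelated to TTR". Severity therefore classifies symptoms that have already met the onset rule; a change in severity is not itself an event. Ongoing and past symptoms are tabulated by severity, but only at enrollment/baseline.

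Section 8.2.4 names no denominator, so the general rules apply:

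- SAP 8.1: "Qualitative variables will be summarized by frequency counts and percentages".
- SAP 8.1: "Unless otherwise specified, the calculation of proportions will be based on non-missing values".
- SAP 7: "Patients with missing data for a variable will be excluded from the denominator".

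No readable rule restricts a denominator to patients free of the symptom at baseline.

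Three other places bear on the point. One objective in SAP 2.2 is: "Enhance the understanding of disease natural history, including the variability and progression of the hereditary and acquired forms of the disease". SAP 5.4, on changes of phenotype, assumes that phenotype-related symptoms persist even when they are not apparent at a visit. Protocol 11.4.1 lists "Progression/worsening of underlying disease" among its examples of adverse events, and that section of the protocol concerns tafamidis-treated patients.

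**The concern.** A patient who already has neuropathic pain at baseline is not missing for that symptom, so the default rules keep that patient in the denominator. Unless the database assigns a new onset date to a recurrence or a worsening, the patient can never enter the numerator. The more common a symptom is at baseline, the rarer its development appears.

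Unequal baseline prevalence is likely in these tables for two reasons that the documents themselves give:

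- **Phenotypes are defined by symptoms (SAP 5.4).** Predominantly neurologic patients generally qualify through ongoing neurologic or gastrointestinal symptoms. Variant patients with a predominantly cardiac phenotype qualify through rhythm disturbance, heart failure or dyspnea. The core symptoms are therefore concentrated at baseline in the columns meant to show their development.
- **One patient can contribute to both sets (SAP 5.2 and 5.3).** For someone who starts tafamidis after enrollment, a symptom acquired before the first dose counts as developed in the untreated set and is already present when the treated set begins. Among these patients, the share with a past or ongoing record of a symptom cannot be lower at first dose than at enrollment.

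At stake is how a natural-history table is read. A column whose patients enter later in their disease can appear to acquire fewer symptoms simply because they already have them. A mild symptom that becomes severe need not appear in these tables at all.

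**Working it through.** The plan states no symptom percentage, prevalence, sample size or power, so there is no figure of its own to reproduce. The arithmetic below is illustrative and every input is an assumption.

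**Inputs**

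- p: share of the set with the symptom at baseline, varied from 10% to 90%.
- q: incidence among patients without it at baseline, mainly 20%, with 10% and 40% as alternatives.
- w: share of patients with the symptom at baseline in whom it worsens, 20% to 40%.
- A patient who already has the symptom gets no new onset date for it.

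**Step 1: dilution within one column.** Percentage over all non-missing patients = (1 − p) × q. Percentage among patients at risk = q.

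| p | shown when q = 20% | at-risk percentage |
|---|---|---|
| 10% | 18% | 20% |
| 30% | 14% | 20% |
| 50% | 10% | 20% |
| 70% | 6% | 20% |
| 90% | 2% | 20% |

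In counts: of 100 patients, 60 have the symptom at baseline and 8 of the other 40 develop it. The default rule gives 8/100 = 8%; the at-risk rule gives 8/40 = 20%.

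**Step 2: two columns with the same q.** The ratio of displayed percentages is (1 − p₂)/(1 − p₁), whatever q is.

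| q | p₁ | p₂ | shown 1 | shown 2 | ratio |
|---|---|---|---|---|---|
| 20% | 40% | 40% | 12% | 12% | 1.00 |
| 20% | 50% | 60% | 10% | 8% | 0.80 |
| 20% | 30% | 60% | 14% | 8% | 0.57 |
| 40% | 30% | 70% | 28% | 12% | 0.43 |
| 20% | 20% | 80% | 16% | 4% | 0.25 |

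**Step 3: two columns with different q.** If column 1 has p = 30% and q = 10%, it shows 0.7 × 10% = 7%. If column 2 has p = 60% and q = 20%, it shows 0.4 × 20% = 8%. A twofold difference in risk appears as 8/7 = 1.14, and the column with the higher prevalence still looks slightly worse. Which column looks better therefore cannot be deduced from prevalence alone.

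**Step 4: worsening.** Onset or worsening over the whole set = (1 − p) × q + p × w. With q = 20% and w from 20% to 40%:

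| p | onset only | onset or worsening |
|---|---|---|
| 30% | 14% | 20% to 26% |
| 50% | 10% | 20% to 30% |
| 70% | 6% | 20% to 34% |

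**The case against.** **The denominator is an inference.** Section 8.2.4 never says that it uses the whole set. The analysis variable might be treated as undefined for someone who already has the symptom. That is possible, but nothing readable says so, and the only stated exclusion is for missing data. The inference is reasonable, and an explicit sentence is needed under either reading.

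**The onset-date rules are not visible.** Symptom entry follows separate CRF completion guidelines, and return visits collect changes in symptoms. A resolved symptom that recurs, or one that worsens, might receive a new onset date. This stands as a condition on the point. For phenotype-related symptoms, the persistence assumption in SAP 5.4 favors treating a patient with a past record as not at risk.

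**A reader might infer that the tables favor tafamidis,** because treated patients are symptomatic and the untreated set includes carriers. The documents do not support that as a conclusion. They give no prevalences. SAP 4 states no hypotheses and makes all analyses descriptive, and no treated-versus-untreated contrast is planned. The tables are also split by phenotype, with asymptomatic carriers separate, so carrier mix matters mainly in the overall columns. The polyneuropathy indication quoted in the protocol specifies symptoms, but the quoted cardiomyopathy indications do not, and the cardiac phenotype admits wild-type patients without symptoms.

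**A reader might also infer that worsening is never counted anywhere.** That goes too far. Treated patients have the adverse-event route. Yearly ECG summaries for cardiac and mixed patients, hospitalizations, deaths and switches to mixed phenotype show other aspects of progression, including in untreated patients. Redacted outputs may cover more. What remains is narrower: no readable symptom table shows a change in severity, and the adverse-event summaries in SAP 8.2.6 use the treated set, so they offer no untreated counterpart.

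**Baseline prevalence is tabulated in the same section.** This helps a careful reader, but those tables are split by ongoing or past status, relatedness and severity. They do not directly give the number at risk with later data.

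**Conclusion.** The point holds as a weakness in how the post-baseline symptom percentages are defined. Under the SAP's default rules each percentage is lowered by the factor (1 − baseline prevalence): an assumed 20% risk would show as anything from 18% to 2% as prevalence runs from 10% to 90%. Columns with different baseline prevalence, whether overall sets or phenotypes, cannot be compared on these percentages. Where prevalence is equal, the comparison between columns is undistorted, although both percentages are still too low as estimates of risk.

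This rests on two assumptions: that the defaults in SAP 7 and 8.1 govern 8.2.4, and that existing symptoms do not acquire new onset dates. The actual size, and the direction of any difference between treated and untreated columns, cannot be computed from the documents. The descriptive nature of the study does not remove the problem, because a percentage with an unsuitable denominator describes the patients poorly. It does limit the consequence: this is a cheap improvement to one family of tables.

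**What to change.** In SAP 8.2.4:

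1. For each symptom, base the post-baseline percentage on patients in that set and phenotype who have no past or ongoing record of the symptom at the set's baseline and at least one later assessment. Show the at-risk n and the follow-up time beside it, since a cumulative percentage also depends on how long patients were observed.
2. Optionally, for patients with the symptom ongoing at baseline, tabulate baseline severity against severity at the yearly visit windows of Appendix 2. Worst-ever severity should not be used, because it rises with the length of follow-up and the number of visits, and untreated follow-up ends at the first dose.

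The section should also say how recurrence and worsening of a recorded symptom are dated, and whether the minimum subgroup size of 10 in SAP 8.1 applies to the at-risk n.

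No new data collection appears necessary: symptoms are recorded at baseline and at return visits, and 8.2.4 already relies on onset date and severity. The cost of item 1 is a few sentences, denominators that vary by symptom, and some extra table rows. Item 2 costs more, because it repeats over sets, phenotypes, relatedness classes and symptoms, which is why it is optional.

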### 8.2.5 Efficacy Analyses

There are no specific efficacy endpoints collected in this study only safety and CCI, see sections 6.2 and 6.3.

### 8.2.6 Safety Analyses

#### Survival Analyses

Mortality will be analysed using the Kaplan Meier method with median survival times (if estimable) and 95% CIs if the number of events are at least 5.

Mortality will be summarized and presented by plots for the following sets: tafamidis treated set by phenotype at enrollment and overall, tafamidis untreated set by phenotype at enrollment and overall, CCI and either predominantly cardiac or mixed phenotype at enrollment, tafamidis treated set for patients who had severe hepatic impairment at baseline, tafamidis

untreated set by their liver transplantation status (liver transplant prior to enrollment/liver transplant after enrollment/no liver transplant), tafamidis treated set by liver transplantation status (liver transplant prior to first dose of tafamidis/liver transplant after the first dose of tafamidis/no liver transplant).

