## 5.3 TAFAMIDIS TREATED

The tafamidis treated set will include the following:

[figure not shown]
- All available data from the enrollment date until final treatment discontinuation of tafamidis or end of follow-up in THAOS (whichever is earlier) for patients who have been enrolled in THAOS, signed the informed consent and who were on tafamidis treatment on or prior to the date of enrollment in THAOS.
- All available data from first dose of tafamidis until final treatment discontinuation of tafamidis or end of follow-up in THAOS (whichever is earlier) for patients who were not on tafamidis at the time of enrollment in THAOS but subsequently initiated treatment with tafamidis.

Note: A patient can be considered part of both the tafamidis untreated and tafamidis treated sets if the patient initiated treatment with tafamidis after beginning participation in THAOS.

The below schematic will help to better understand the patient population to be analysed:

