**The other subgroups to be considered are as follows:**

- CCI [REDACTED]
- Severe hepatic impairment (only to be used corresponding to tafamidis treated set). The patients with severe hepatic impairment at baseline will be identified by any of the following:
  - The following pre-coded terms on the Gastrointestinal medical history and the Gastrointestinal general assessment forms: Hepatitis, Cirrhosis, Gastrointestinal malignancy, Hepatotoxicity, Other hepatic impairment having severity scale as “severe”.
  - The following terms appearing in the database as entered on the Other Gastrointestinal Medical History or General Assessment forms at baseline and assessed as ‘severe’: “severe impaired hepatic function”, “severe hepatic dysfunction”, “severe liver dysfunction/liver failure”. Other similar terms as identified during the final database lock of this study may be investigated to identify patients with severe hepatic impairment at baseline.
- Patients not on tafamidis at the time of enrollment on THAOS who had a liver transplant prior to enrollment on THAOS
- Patients not on tafamidis at the time of enrollment on THAOS who had a liver transplant after enrollment on THAOS
- Patients not on tafamidis at the time of enrollment on THAOS without any liver transplant either before or after enrollment on THAOS
- Patients treated with tafamidis at any time in THAOS and with a liver transplant prior to first dose of tafamidis
- Patients treated with tafamidis at any time in THAOS and with a liver transplant after the first dose of tafamidis
- Patients treated with tafamidis at any time in THAOS and never had a liver transplant
- Off-label use of 80/61 milligram (mg) of tafamidis (only to be used corresponding to tafamidis treated set) defined as:
  - Patients not classified as predominantly cardiac or mixed phenotype at the first date of dosing with a dose of 80/61 milligram (mg) of tafamidis.
- Predominantly neurologic at baseline who become mixed phenotype post baseline\*
- Predominantly cardiac at baseline who become mixed phenotype post baseline\*

Sample size in a subgroup needs to be at least 10 in order to have sufficient data to provide descriptive statistics, listings will be provided for smaller subgroups.

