#### **6.2.1 Survival**

Survival will be analysed as time from enrollment or first dose of tafamidis, for the untreated and tafamidis treated set respective until the time of death. Patients who are still alive at the end of the analysis period (start of tafamidis or end of follow-up in THAOS for the untreated set or last dose of tafamidis in the tafamidis treated set) will be censored.

CCI [Redacted]

[Redacted]

[Redacted]

[Redacted]

- [Redacted]
- [Redacted]
- [Redacted]

CCI [Redacted]

[Redacted]

[Redacted]

[Redacted]

PFIZER CONFIDENTIAL

[Redacted]

CCI

[Redacted]

[Redacted]

[Redacted]

CCI

[Redacted]

[Redacted]

[Redacted]

[Redacted]

[Redacted]

CCI

[Redacted]

[Redacted]

PFIZER CONFIDENTIAL

[Redacted]

CCI [Redacted]

CCI [Redacted]

[Redacted]

[Redacted]

[Redacted]

[Redacted]

[Redacted]

[Redacted]

- [Redacted]
- [Redacted]
- [Redacted]
- [Redacted]

PFIZER CONFIDENTIAL

[Redacted]

CCI [Redacted]

[Redacted]

[Redacted]

[Redacted]

- [Redacted]
- [Redacted]
- [Redacted]
- [Redacted]
- [Redacted]
- [Redacted]

[Redacted]

- [Redacted]
- [Redacted]

[Redacted]

[Redacted]

CCI [Redacted]

[Redacted]

[Redacted]

[Redacted]

CCI [REDACTED]

CCI [REDACTED]

CCI [REDACTED]

[REDACTED]

[REDACTED]

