### Deaths

Summaries on the number (%) of patients who died, by primary cause, and whether deaths were ATTR related will be provided using all enrolled patients, tafamidis treated set by phenotype at enrollment and overall, tafamidis untreated set by phenotype at enrollment and overall, CCI [REDACTED] and either predominantly cardiac or mixed phenotype at enrollment, tafamidis treated set for patients who had severe hepatic impairment at baseline, tafamidis treated set by liver transplantation status (liver transplant prior to first dose of tafamidis/liver transplant after the first dose of tafamidis/no liver transplant), tafamidis untreated set by their liver transplantation status (liver transplant prior to enrollment/liver transplant after enrollment/no liver transplant).

A separate listing of deaths will also be provided for the tafamidis treated set.

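### Survival by liver-transplant status groups patients by a transplant that occurs after the clock starts, so the 'after' curve contains immortal time and the 'none' curve loses it

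*SAP*

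**What the plan says.** **Objective.** SAP 2.2 (and Protocol section 8) includes: "Compare the progression of disease and overall survival in patients with ATTR amyloidosis with and without liver transplant".

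**Clock.** SAP 6.2.1: "Survival will be analysed as time from enrollment or first dose of tafamidis, for the untreated and tafamidis treated set respective", running until death. Survivors are censored at the end of the analysis period, which is "start of tafamidis or end of follow-up in THAOS for the untreated set or last dose of tafamidis in the tafamidis treated set".

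**Groups.** SAP 8.2.6 (Survival Analyses) asks for Kaplan-Meier plots, medians and 95% CIs for the "untreated set by their liver transplantation status (liver transplant prior to enrollment/liver transplant after enrollment/no liver transplant", and for the treated set by transplant before first dose, after first dose, or none. SAP 5.4 defines the *after* groups as "Patients not on tafamidis at the time of enrollment on THAOS who had a liver transplant after enrollment on THAOS" and "Patients treated with tafamidis at any time in THAOS and with a liver transplant after the first dose of tafamidis". Neither has a time limit. The untreated *none* group requires no transplant before or after enrollment.

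**Treated-set data.** For patients who start tafamidis after enrollment, SAP 5.3 includes "All available data from first dose of tafamidis until final treatment discontinuation of tafamidis or end of follow-up in THAOS (whichever is earlier". The note closing the safety part of 8.2.6 names deaths among the events summarized up to 28 days after the last dose.

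**Death counts.** The Deaths paragraph of 8.2.6 uses the same grouping: "tafamidis untreated set by their liver transplantation status (liver transplant prior to enrollment/liver transplant after enrollment/no liver transplant".

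The readable text has no landmark, delayed entry, clock restart or change of group at transplant.

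**The concern.** Two of the three groups are defined by the future. Time between the clock start and transplant is counted as *after* follow-up, although no death can occur in it by construction. Deaths among patients still waiting go to *none*. This is immortal-time bias. It does not shrink as the registry grows: more patients only narrow the confidence interval around a distorted curve.

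This is the only readable time-to-event analysis serving the transplant objective, and both documents say survey data may inform treatment guidelines. The *prior* groups have no immortal time after time zero, but they contain only patients who survived to it, and the SAP does not say so.

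Censoring adds two problems.

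- A transplant after tafamidis start (untreated set) or after the last dose (treated set) still places a patient in *after*, although all the time counted for that patient is free of death.
- In the treated set, a death after transplant counts only while the patient is on tafamidis or, at most, within 28 days of the last dose. Section 6.2.1 and the note in 8.2.6 differ on which.

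**Working it through.** The documents give no event count, expected survival or transplant rate for these curves, so there is no planned figure to reproduce.

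**Direction (no assumptions on rates).** At each death time let *n_pre* be patients who will be transplanted later, *n_post* those already transplanted and *n_none* those never transplanted. All deaths in *after* come from *n_post*.

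- *After*: the SAP uses d_after/(n_pre + n_post), a time-dependent split uses d_after/n_post. The SAP's hazard is never larger.
- *None*: the SAP uses d_none/n_none, a time-dependent split uses d_none/(n_none + n_pre). The SAP's hazard is never smaller.

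The product-limit curves are therefore ordered as stated, with equality only if no relevant death occurs while anyone is waiting. In 2,994 simulated data sets, with transplant effects from strongly protective to strongly harmful, a Cox ratio from the fixed groups never exceeded the time-dependent one.

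**Size (illustration).** Inputs:

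- Exponential survival with mean 10-15 years. This is Protocol 7.1's figure for ATTR-PN from first symptoms, applied here from time zero, so λ = 1/15 to 1/10 per year.
- Assumed, not in the documents: no transplant effect, equal risk, candidate share p = 10-30%, follow-up ending uniformly over 1-12 years, and transplant timing with distribution F and density f.

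Let S(t) = exp(−λt)·G(t), where G is the probability that follow-up has not ended, and W(t) = ∫ from t onward of f(u)S(u)du, the candidates whose transplant is still to come. Then

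- h_after(t) = λSF / (SF + W)
- h_none(t) = λS(1 − pF) / [S(1 − pF) − pW]
- 5-year survival = exp(−∫₀⁵ h), with truth exp(−5λ).

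Example: mean 12.5 years (λ = 0.08), p = 20%, transplants uniform over 2 years. At t = 1, SF = 0.462 and W = 0.424, so h_after = 0.08 × 0.462/(0.462 + 0.424) = 0.042, about half the true 0.08. At 5 years *after* shows 72.5% and *none* 65.8%, where both should be exp(−0.4) = 67.0%.

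Over the full ranges:

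| Transplants fall | *After* 5-year survival too high (points) | *None* too low (points) | Immortal share of *after* time |
|---|---|---|---|
| within 6 months | 1.2-1.5 | 0.1-0.6 | 5% |
| within 1 year | 2.4-3.1 | 0.3-1.2 | 9-10% |
| within 2 years | 4.8-6.2 | 0.5-2.3 | 18-19% |
| within 3 years | 7.2-9.3 | 0.7-3.1 | 24-26% |
| within 5 years | 12.0-15.6 | 1.0-4.3 | 35-36% |
| at a constant 3-20% per year | 12.4-20.9 | 0.2-3.2 | 38-48% |

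Splitting person-time at transplant removes the error in every equal-risk scenario.

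**Sicker candidates.** Give candidates hazard 2λ, with S_c and W_c formed from 2λ. Then h_none = [(1−p)λS + 2pλS_c(1−F)] / [(1−p)S + p(S_c(1−F) − W_c)]. With mean 10 years, p = 30% and transplants within 5 years, *none* shows 53.0% at 5 years. A time-dependent *no transplant* curve shows 56.4%, and non-candidates have exp(−0.5) = 60.7%. The curve is thus about 8 points below non-candidates; about 3.5 of these come from the fixed grouping and the rest from the candidates' own risk. Here *after* shows 57.0%, above *none*, although recipients carry twice the hazard. With transplants within 6 months the order reverses, at about 39% against 59%.

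**The case against.** **Descriptive only.** SAP section 4 states no hypotheses. That is true, but the plotted curves and medians are themselves distorted, and a stated objective is to compare them.

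**Size unknown, possibly 1-2 points.** This stands. The illustration rests on assumed timing and candidate share, and on an ATTR-PN survival figure, while the groups pool wild-type disease, asymptomatic carriers and all phenotypes. The direction of the component does not depend on those inputs.

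**The curves may never appear.** Groups under 10 patients become listings, and under 5 events there is no Kaplan-Meier estimate (SAP 5.4, 8.1). This limits the harm, but the plan cannot know in advance that it will apply.

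**Redaction.** Parts of the SAP cannot be read. The survival definition and the transplant groups can be, and the point rests on those.

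Four stronger readings are tempting, and the documents do not support them.

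- *The published contrast must favour transplant.* Confounding by indication and case mix can act either way, as the last example shows.
- *If recipients stop tafamidis at transplant, no treated-set death can be observed.* This reads 6.2.1 alone. The 28-day note names deaths, so early post-transplant deaths may count.
- *The plan will report a biased hazard or rate ratio.* The readable SAP plans none between transplant groups; only the curves, medians and death counts are at issue.
- *The 'none' curve is never more than about 4 points low.* That bound belongs to the equal-risk case with 10-30% candidates.

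**Conclusion.** The concern holds. *After* and *none* are fixed by an event after time zero, in both analysis sets, with no correction in the readable text. Relative to a time-dependent classification of the same patients, the shift is never away from transplant. It is small if transplants follow time zero within months and large if they are spread over years. The point figures depend on the assumptions listed; the ordering does not. The net direction of *after* against *none* cannot be stated from the documents. Because the curves serve a named objective and the data needed to correct them are in hand, this should be changed before the final analysis.

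**What to change.** In SAP 5.4 and 8.2.6:

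1. Count each patient as *no transplant* until the transplant date, then enter them in *post-transplant* with delayed entry (Simon-Makuch, or extended Kaplan-Meier). A prespecified landmark is an alternative, though it describes a different population.
2. Count only transplants within the set's analysis period.
3. Reconcile censoring at last dose (6.2.1) with last dose plus 28 days (note in 8.2.6) for the treated-set curves.
4. State the time zero for patients already on tafamidis at enrollment. Section 6.2.1 says first dose, 5.3 starts their data at enrollment, and Appendix 2 brings in the consent date. For these patients a transplant after first dose could precede enrollment.
5. Label the death counts by transplant status as not comparable across groups.
6. State that the *prior* groups include only survivors to time zero, and that splitting time does not remove confounding by indication or case-mix differences.

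The cost is SAP wording and modest reprogramming. Transplant dates are already on the case report form (SAP Table 2). Early post-transplant risk sets will be small, and some groups may become listings or get no Kaplan-Meier estimate under the existing rules of at least 10 patients and at least 5 events.
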